6.2 Aqueous Lidocaine and Placebo Perineal Application

Once subjects have a confirmed diagnosis of their gynecologic cancer, and they complete the survey packet at their 12-week follow-up visit, they will be randomized to receive a solution containing either aqueous lidocaine or a placebo. They will also be given a package of cotton balls with instructions to put the solution on three cotton balls and apply them to the perineum/vaginal introitus for one minute prior to sexual intercourse. Subjects will be asked to document in their diary successful or unsuccessful application of the perineal solution. They will also be asked to complete a visual pain scale for each sexual encounter. Subjects will be reminded to bring the calendars to the return visit with a phone call.

The aqueous lidocaine/placebo solution will be supplied by the Investigational Drug Service. It will be labeled in a manner that does not identify the presence of active ingredient.

CALENDAR/SCHEDULE OF EVENTS

Procedures	Visit 1 Pre-surgery	Visit 2 (12 weeks post- surgery)	Visit 3 (24 weeks post-surgery)	Visit 4 (32 weeks post-surgery)
Informed Consent	x			
Inclusion / Exclusion Criteria	x			
Performance Status	x	x	x	x
Physical Exam	x	x	x	x
Questionnaires	x	x	x	x
Diary of Sexual encounters and lidocaine/placebo usage		x	x	x
Randomization		x		

7. Safety

7.1 Possible Adverse events of lidocaine include:

- Rare allergic reactions: Itching; hives; edema of the face or hands; tingling in the mouth or throat or chest tightness (which can cause trouble breathing).
- Other uncommon reactions: Blurred or double vision; confusion; dizziness; lightheadedness; or drowsiness; chest pain or an uneven heartbeat; skin rash; swelling in the area where this medicine is applied; and trembling (shaking).

7.2 Other risks of the study procedures include:

- Embarrassment: discomfort answering some of the questions of the surveys (subjects may skip any questions they choose).

7.3 Stopping Rules:

- Subject may stop participating at any time
- Subject not following instructions
- Gel becomes unavailable
- Attending physician decision to withdraw subject
- Breach of confidentiality

8. Statistical Evaluation/Considerations

The primary objective of this double-blinded, randomized, placebo-controlled study is to assess the relative efficacy of aqueous lidocaine solution in improving sexual functioning within the population of females undergoing a primary surgical procedure for the treatment of ovarian, endometrial, and cervical cancer. Sexual functioning will be assessed using the self-reported Female Sexual Function Index (FSFI; full scale score ranges from 2 to 36 where scores <26 are indicative of sexual dysfunction). Given the lack of existing literature pertaining to sexual functioning immediately following surgical intervention, this will be a pilot study aimed at obtaining estimates of relative efficacy as well as assessing feasibility. Existing literature on sexual functioning in gynecologic cancer survivors, assessed a year or more post-surgery, provide median and mean estimates ranging between 16.6-17.2 and 19.75-19.9 (SD 7.0-9.8), respectively, on the FSFI full scale [6, 7, 8, 9]. We anticipate sexual functioning will be even lower in the 24 weeks immediately following surgery. A sample size of 15 patients per treatment group achieves 80% power to detect an increase of 9.3 between the null hypothesis that both group means are 17.0 and the alternative hypothesis that the mean of the aqueous lidocaine solution treatment group is 26.3 with estimated group standard deviations of 10.0 and a significance level of 0.05. Power calculations were based on using a one-sided two-sample t-test for a single point in time while assuming the actual distribution of the FSFI full scale is normal. Accordingly, 30 patients from each cancer type—ovarian, endometrial, and cervical—will be recruited for a total of 90 subjects.

To assess changes in sexual, physical, psychological, and social domains, linear mixed effects regressions models will be utilized. Random effects will be employed to account for the longitudinally correlated nature of repeated questionnaire measurements.

9. Data Collection and Record Keeping

9.1 Data will be collected primarily by paper forms that include reported information from each study participant. Information will be transferred to electronic database collection documents for use by the statisticians without any identifiable information.

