 - Hypothesis: Subjects surgically treated for ovarian, peritoneal, fallopian tube, cervical or endometrial cancer will have higher sexual functioning and less pain associated with sexual encounters after perineal treatment with aqueous lidocaine.
- Secondary objectives include characterizing the pre and post-treatment functioning of gynecologic cancer survivors with respect to physical, psychological, and social dimensions.
 - Subjects will complete nine short surveys (The Female Sexual Function Index, The PHQ-9, the GAD-7, the SPS, Rosenberg's Body Self-Esteem Index, the Severity of PTS Symptoms Scale, the Adverse Childhood Events Index, the SF-12, and the Dyadic Adjustment Scale) at their initial visit, assessing physical, psychological, and social elements related to sexuality. The same packet of surveys will be completed twelve weeks following surgery, after which, they will be randomized to a blinded perineal intervention. Survey packets will be completed 12 and 24 weeks following randomization to the perineal intervention.
 - A visual pain scale will be completed after each sexual encounter.
 - A diary documenting frequency of sexual encounters will be collected.

4. Study Population

Subjects comprising this study population include women undergoing initial consultation at the University of Iowa Hospitals and Clinics/Holden Comprehensive Cancer Center for a documented or suspected diagnosis of ovarian, fallopian tube, peritoneal, endometrial or cervical cancer. Each subject must be scheduled to undergo surgical treatment for their disease prior to enrollment. Enrollment will be offered and consent obtained by the Investigator or one of the sub-Investigators at the time of initial consultation in the outpatient clinic.

Subjects ultimately diagnosed with one of the previously mentioned gynecologic malignancies will remain eligible to continue on the trial, while those found to have no evidence of cancer will be excluded.

Inclusion/Exclusion Criteria:

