5.2.3 Evaluation of sexual dysfunction

The survey packet evaluates physical, psychological, and social elements related to sexuality. Each packet will be assembled into a large envelope and handed to the subject by the healthcare provider in the UIHC Gynecologic Oncology outpatient clinic. The surveys will be completed by the subject in the clinic (in a private area) on the day of the visit and then collected by the research data managers.

Each survey packet will contain:

1. Female Sexual Function Index: A self-report measure of sexual functioning
2. Patient Health Questionnaire 9 (PHQ-9): Instrument for screening, diagnosing, monitoring, and measuring the severity of depression.

3. Generalized Anxiety Disorder 7-item scale (GAD-7): A brief measure for assessing generalized anxiety disorder.
4. Social Provisions Scale (SPS): Instrument to assess provisions of social relationships.
5. Rosenberg's Body Self-Esteem Index: Scale that measures global self-worth by measuring both positive and negative feelings about the self.
6. Severity of Posttraumatic Stress Symptoms-Adult: Assesses the severity of posttraumatic stress disorder following a particular event or experience.
7. Adverse Childhood Events Index: A scale measuring types of physical, verbal, and emotional childhood trauma
8. SF-12: A generic measure of health status
9. Dyadic Adjustment Scale: A relationship adjustment self-report measure.

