5.2.4 Diary of Sexual Encounters

A diary of sexual encounters during the 24 weeks of observation will be kept by participating subjects. On the calendar, subjects will be asked to document date of sexual encounter and an accompanying successful or unsuccessful perineal application of the intervention. For each encounter, subjects will also be asked to mark a visual pain scale.

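### Section 7.3 does not separate stopping the solution from leaving follow-up, so removing randomised women for non-adherence can bias the arm comparison

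*Combined protocol and SAP*

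**What the plan says.** Section 7.3 (Stopping Rules) is a single list of five short items. It opens with "Subject may stop participating at any time", continues with "Subject not following instructions" and "Gel becomes unavailable", and then gives "Attending physician decision to withdraw subject" and breach of confidentiality. Not following instructions has no definition, threshold or assessor. The list does not say whether an item ends use of the solution, outcome collection, or both.

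Elsewhere, failed application is expected and recorded. Section 6.2 states: "Subjects will be asked to document in their diary successful or unsuccessful application of the perineal solution". Sections 5.1.3 and 5.2.4 say the same of the diary.

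Outcome collection depends on attendance. On the questionnaires, Section 5.2.3 says "The surveys will be completed by the subject in the clinic (in a private area) on the day of the visit". Sections 5.1.2 and 5.1.3 have the pain scales and diaries collected at the three-monthly visits. Only two packets follow randomisation; Section 3 says "Survey packets will be completed 12 and 24 weeks following randomization to the perineal intervention".

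Section 8 names linear mixed models with random effects. It states no analysis population, no handling of missing data and no allowance for dropout.

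**The concern.** The question is lidocaine v placebo as randomised. Whether a woman keeps applying the solution is decided after randomisation. It can depend on numbness or irritation, on lack of benefit, or on pain, all of which may be related to arm and to sexual function. If such women leave follow-up, those who remain are a selected group, and the selection can differ between arms.

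The loss would also be hard to recover. Packets are completed in clinic and diaries are handed in at visits, so a woman removed before Visit 3 has no FSFI after randomisation. Pain and encounter frequency, which Section 3 places in the primary objective beside the FSFI, stop being recorded too. FSFI collection does not need the product, so ending it because supply fails would be an avoidable loss.

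**Working it through.** **The text, side by side.** The items on either side of the two rules speak of ending participation and withdrawing the subject. Removal from the study is therefore the natural reading of the whole list, although it is not stated. The diary sections treat a failed application as an observation. A woman who records one has followed the diary instruction but perhaps not the application instruction. Which of these Section 7.3 refers to is undefined.

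**The plan's own figure.** Inputs from Section 8: 15 per arm within a cancer type, difference 9.3, SD 10.0, one-sided 0.05, two-sample t-test.
- Noncentrality = 9.3 / (10 × √(2/15)) = 2.55 on 28 degrees of freedom.
- Power = 79.9%, so the stated 80% reproduces. It includes no allowance for loss.

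**Loss unrelated to outcome (loss rates assumed).**
- 20% loss leaves 15 × 0.8 = 12 per arm. Noncentrality = 9.3 / (10 × √(2/12)) = 2.28 on 22 degrees of freedom, and power = 71.3%.
- At 10% and 30% loss, power is 76.0% and 65.9%.

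**Loss related to outcome (removal rates and correlation assumed).** Take SD 10 and no true effect. In each arm a fraction p is removed according to a latent adherence variable that has correlation r with FSFI, lower scores leaving first. The mean of those remaining rises by

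shift(p, r) = 10 × r × φ(z_p) / (1 − p),

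where z_p is the normal quantile at p and φ is the normal density. The ratio φ(z_p)/(1 − p) is 0.195, 0.350 and 0.497 for p = 10%, 20% and 30%.

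| Removed, one arm v the other | r = 0.3 | r = 0.5 |
|---|---|---|
| 20% v 20% | 0 | 0 |
| 20% v 10% | 10 × 0.3 × (0.350 − 0.195) = 0.5 | 10 × 0.5 × 0.155 = 0.8 |
| 30% v 10% | 10 × 0.3 × (0.497 − 0.195) = 0.9 | 10 × 0.5 × 0.302 = 1.5 |
| 10% v none | 10 × 0.3 × 0.195 = 0.6 | 1.0 |
| 30% v none | 1.5 | 10 × 0.5 × 0.497 = 2.5 |

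Values are FSFI points in favour of the arm that loses more women. With r = 0 every entry is zero. If the mechanism itself differs between arms, equal removal rates no longer guarantee zero.

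**Effect of adjusting for earlier scores.** FSFI is also collected at Visits 1 and 2, before the solution is used. Take 20% v none with r = 0.5, where the raw shift is 10 × 0.5 × 0.350 = 1.75.
- If removal depends only on earlier observed FSFI, adjustment brings the shift to about 0.
- If removal depends on the later outcome itself, and an earlier score has correlation ρ with it, about 1.75 × (1 − ρ²) remains. That is 1.3 for ρ = 0.5 and 0.9 for ρ = 0.7 (both assumed).

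**The case against.** The strongest reply is that Section 7.3 is five terse items under a safety heading. It does not say that removal is automatic or that outcome collection ends. That is correct: the documents are silent. But nothing in them provides for follow-up after stopping, and the neighbouring items point towards withdrawal, so the silence has to be resolved whichever meaning was intended.

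Four stronger readings are tempting, and the documents do not support them.
- *The arm comparison is biased.* Bias requires loss that is related to outcome and differs by arm in rate or mechanism. Blinding limits differences driven by investigators, though not women's own responses to the solution. Bias is possible, not established.
- *Section 7.3 contradicts the diary.* Recording a failed application is itself following an instruction. The passages are in tension over an undefined term.
- *Encounter frequency is inflated because low users are removed.* The solution is applied before intercourse, so a woman with few encounters breaks no application instruction.
- *A supply stop is also selective.* One Investigational Drug Service supplies both blinded products, and no link to arm or outcome is stated. On its face this costs precision.

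It is also fair to say that the shifts above are for raw completer means, whereas Section 8 plans mixed models. Those use earlier visits and are valid if loss depends only on observed scores. This reduces the concern but does not remove it, because loss may depend on tolerability or pain that the FSFI history does not capture. Section 8 calls the trial a pilot, but obtaining estimates of relative efficacy is one of its stated aims, and a shift in the estimate matters there even without a formal test.

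**Conclusion.** The point holds as a weakness in a stated rule. Section 7.3 mixes reasons to stop the solution with reasons to leave the study, and its natural reading drops randomised women for a post-randomisation reason that can depend on arm and outcome. The arm comparison can be biased in either direction.

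The size cannot be derived from the documents, which give no withdrawal rate. Under the stated assumptions the completer-mean shift runs from zero, for equal loss by the same mechanism, to 1.5 points for 30% v 10%. Removal in one arm only, at 10% to 30%, gives 0.6 to 2.5 points. These compare with a design difference of 9.3, and the mixed model reduces them to the extent that loss depends on observed scores.

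A reader might turn the one-arm case into a sharply raised type I error. That would rest on removal confined to one arm and an unadjusted test of completers, which is not the planned analysis, so no such figure is claimed here. The loss of power, from 80% to about 71% per cancer type at 20% loss, needs no assumption about selection.

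**What to change.** - In Section 7.3, list separately the reasons the study solution stops and the reasons follow-up stops.
- Record not following instructions as adherence data, with a definition, and not as a reason to end outcome collection.
- After non-adherence or supply failure, continue the scheduled Visit 3 and Visit 4 packets and the encounter diary for women who still consent.
- State in Section 8 that all randomised women are analysed in their assigned arm whatever their use of the solution.
- Leave consent withdrawal, attending-physician withdrawal and breach of confidentiality in place. Keep packets in clinic, so that the immediate PHQ-9 review in Section 5.2.5 is unchanged.
- Reconcile the *gel* of Section 7.3 with the *solution* named elsewhere.

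These changes concern data collection and analysis. They leave open when the solution itself should stop.

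The cost is wording in Section 7.3 and one sentence in Section 8, with no added visits or patients. The small downside is that outcomes from women off the solution dilute the estimated effect.
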